4.2 Discontinuation and Withdrawal of Subjects

Subjects who discontinue treatment during the study will be encouraged by investigators to continue to participate in all scheduled study site visits and assessments, and study data will be collected for these subjects per protocol. Study drug administration may be stopped early at the discretion of the investigator (or designee) if a subject does not tolerate the dosing regimen. Every effort should be made to keep subjects in the study.

Early withdrawal of a subject from the study (before Week 12) will initiate procedures for ending all subject participation in the study, including EOT and EOS assessments (Section 4.2.2). For subjects who are withdrawn early, an EOT visit should be conducted within 2 weeks after the last day of study drug. After completing the EOT visit, an EOS phone visit should be completed within 2 weeks after completing the EOT visit. The duration of the study is defined for each subject as the date signed written informed consent is provided through the EOS phone visit. The Sponsor may continue to enroll subjects to account for discontinuations, withdrawals, early terminations, etc.

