3.1.8 Analysis Visit Windows

Visit windows for study conduct are specified in Table 1: Schedule of Activities. Unless otherwise specified, the following analysis visit rules will be implemented for all endpoints [REDACTED] and seizure diary (see sections 3.8.3, 3.8.4, and 3.9.6 for analysis visit window computations). For all unscheduled visits and end of treatment (EOT) visits from subjects discontinuing treatment early (before Week 12), assessments will be mapped according to the analysis visit windows in Table 2 for primary summarization and analysis. If the visit does not fall within any of the analysis visit windows, then the visit will be considered missing at the specified time point for analysis purposes.

Table 2: Nominal (Targeted) Time Points and Analysis Visit Windows

Assessment	Nominal (Targeted) Time Point	Analysis Visit Window (Interval in Study Days)
Baseline Assessments	Study Day 1	≤ Day 1
Phone/Titration (Day 6)	Study Day 6	>Day 1 - ≤Day 8
Phone/Titration (Day 11)	Study Day 11	≥Day 9 - ≤Day 21
Week 6 (Study Day 43)	Study Day 43	≥Day 22 - ≤Day 64
Week 12 (Study Day 85)	Study Day 85	≥Day 65 - ≤Day 92
Week 14 (Study Day 99)	Study Day 99	≥Day 93

After mapping the data from unscheduled and end of treatment (EOT) visits from subjects discontinuing treatment early to the nominal time point, the following rules will apply if multiple records are available within a single analysis visit window unless otherwise specified for a particular analysis:

- If a record exists for the nominal time point, that record will be selected for analysis.
- If a record for the nominal time point does not exist and multiple records are available within a single analysis visit window,
 - The record closest to the planned assessment day will be selected for analysis
 - If 2 records are equidistant from the target day, then the earliest record will be selected (does not apply to the Week 12 or 14 visits).
- If a subject has no record in an analysis window, the subject will be considered missing at that time point.

For the primary and key secondary objectives, a supportive analysis will be conducted in which CGI-I-AS assessments from unscheduled visits and end of treatment (EOT) visits from subjects discontinuing treatment early (before Week 12) will be mapped according to the analysis visit windows in Table 3.

Table 3: Nominal (Targeted) Time Points and Alternative Analysis Visit Windows

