If more than 3% of CGI-I-AS values at Week 12 are missing, as a sensitivity analysis, missing data will be imputed using the multiple imputation (MI) procedure. The imputation strategy described in Ouyang (2017) will be implemented for this study. There are only two visits where CGI-I-AS is assessed, hence, there are 2 possible missing patterns in the CGI-I-AS data: 1) Week 6 assessment is missing and Week 12 assessment is present (non-monotone pattern); or 2) Week 12 assessment is missing but Week 6 assessment is present (monotone pattern). In general, the MAR assumption is reasonable for intermittent missing values before a subject is discontinued because the data before and after the intermittent missing value are known. In this case, if Week 6 CGI-I-AS is missing but Week 12 CGI-I-AS is assessed (missing data pattern 1), it is reasonable to consider the missing Week 6 data as MAR. However, missing CGI-I-AS at Week 12 after the subject is withdrawn from the trial may or may not be MAR. Multiple imputation will first be implemented under the MAR assumption. To assess the appropriateness of the MAR assumption, additional sensitivity analyses using a tipping point approach will be performed under scenarios assuming missing not at random (MNAR) for the missing data pattern 2 above.

Multiple Imputation Procedure under MAR assumption will be conducted as follows using SAS PROC MI:

1. Missing Week 6 CGI-I-AS data points will be imputed under MAR assumption using a logistic regression model for ordinal data with randomized treatment, age group, region, and CGI-S-AS Overall Score at Baseline as independent variables.
2. Missing Week 12 CGI-I-AS data points will be imputed under MAR assumption using a logistic regression model for ordinal data with randomized treatment, age group, region, CGI-S-AS Overall Score at Baseline, and the Week 6 CGI-I-AS as independent variables.
3. Thirty complete imputed datasets will be generated by repeating the above steps 30 times.
4. The primary MMRM analysis of CGI-I-AS described above will be performed for each of the 30 complete imputed data sets.

5. The estimated treatment effects will be combined across the 30 analyses using SAS PROC MIANALYZE.

If the treatment effect is significant in the analysis using the MI procedure under MAR, with significance level of 0.05 and more than 5% of CGI-I-AS values at Week 12 are missing, a tipping point analysis will be conducted.

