The tipping point analysis will focus on the imputed CGI-I-AS values which may be MNAR (missing data pattern 2 above). These analyses will start with the 30 imputed datasets created under a MAR assumption as described above. For each dataset, the imputed values of CGI-I-AS for the OV101 group (with missing pattern 2) will be worsened by adding 1 (unless the current value is the highest level on the CGI-I-AS scale [7=very much worse]). The placebo group imputed values will remain unchanged. After the OV101 group's imputed Week 12 CGI-I-AS data have been "worsened" by 1 point for those with missing pattern 2, the MMRM model used in the primary analysis will be fitted to the data and the estimated treatment effects will be combined using SAS PROC MIANALYZE. This process will be repeated, at each step incrementally worsening by 1 the imputed values of CGI-I-AS for the OV101 group, until the treatment effect is no longer significant (p-value for the treatment comparison ≥ 0.05).

As a sensitivity analysis, the following rank-based imputation strategy described in Ouyang (2017) will also be implemented when more than 5% of CGI-I-AS values at Week 12 are missing. This analysis will include both subjects with a Week 12 CGI-I-AS and subjects who discontinued prior to the Week 12 assessment, without the need for multiple imputation methodology and the associated assumptions. This approach assumes that discontinuation from the trial is detrimental so it penalizes the treatment group with more early discontinuations. The subjects will be first divided into 2 sets according to their CGI-I-AS assessments: 1) those with a Week 12 CGI-I-AS; and 2) those with a Week 6 CGI-I-AS but no Week 12 CGI-I-AS. Within the two sets, subjects will be ranked separately (based on the Week 12 CGI-I-AS for set 1 and the Week 6 CGI-I-AS for set 2). The lowest rank will be given to the largest CGI-I-AS within that set. The Wilcoxon Rank-Sum test will then be applied to this ranking instead of ranking solely based on the Week 12 CGI-I-AS for completers.

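### When a child attends Week 6 and then withdraws with an EOT visit on Day 44-64, the exit CGI-I-AS is normally dropped from the primary and dropout analyses, and no planned analysis uses it to rank that child or to inform the missing Week 12 value

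*SAP*

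**What the plan says.** Protocol 4.2 asks for an exit visit: "For subjects who are withdrawn early, an EOT visit should be conducted within 2 weeks after the last day of study drug". SAP 3.1.8 and 3.8.1 both expect CGI-I-AS ratings from such visits and from unscheduled visits.

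For these visits, SAP 3.1.8 states that "assessments will be mapped according to the analysis visit windows in Table 2 for primary summarization and analysis". The Week 6 window is "≥Day 22 - ≤Day 64" and the Week 12 window is "≥Day 65 - ≤Day 92". When two records fall in one window, "If a record exists for the nominal time point, that record will be selected for analysis". Only if there is no such record does the fallback apply: "The record closest to the planned assessment day will be selected for analysis". SAP 4.1.1 points the same way for repeat results at one visit, since it takes the first.

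SAP 3.8.6 then uses these mapped values in four places:

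- The primary MMRM uses the Table 2 visits without imputation.
- The Week 12 imputation model takes treatment, age group, region, "CGI-S-AS Overall Score at Baseline, and the Week 6 CGI-I-AS as independent variables".
- The tipping-point analysis starts from the same 30 imputed datasets.
- The rank analysis orders completers and non-completers separately, "based on the Week 12 CGI-I-AS for set 1 and the Week 6 CGI-I-AS for set 2".

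The same section sets out its missing-data patterns on the premise that CGI-I-AS is rated at only two visits.

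Two supportive analyses treat the exit rating differently. Table 3 maps an early EOT after Day 43 to Week 12, for the primary and key secondary endpoints. The nominal-visit analysis lists EOT together with Day 85 and Week 12.

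**The concern.** Take a child rated 3 on Day 43 who withdraws because of worsening and is rated 6 at an EOT visit on Day 55. Table 2 puts both ratings in the Week 6 window, the scheduled record wins, and the 6 is not used. There is no Week 12 value. The primary MMRM, the imputation, the tipping-point analysis and the rank analysis all work from the 3.

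SAP 3.8.6 itself accepts that a Week 12 score missing after withdrawal may not be missing at random. Yet its imputation model omits the last rating before the gap. The rank analysis is meant to treat leaving the trial as a bad outcome, yet it can place this child among the better non-completers. These are the analyses a reader would use to judge whether dropout explains the primary result, so an observed rating relevant to that question should appear in at least one of them.

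**Working it through.** **1. Which records are affected.** No figure in the plan needs reproducing here, so the check is on the record-selection rules. With Week 6 held on Day 43, an EOT on Day 44-64 falls in the Week 6 window: 64 - 43 = 21 days, out of 85 - 43 = 42 days between the two target visits. I listed every pair of a Week 6 visit day and a later EOT day up to Day 64. The Week 6 visit tolerances are assumptions, because the schedule table is not in the text available. SAP 3.1.8 does not say whether the nominal time point means the scheduled visit or exactly Day 43, so both readings are shown.

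| Week 6 visit tolerance (assumed) | Exit score dropped: scheduled-visit reading | Exit score dropped: exact-Day-43 reading | Exit score becomes Week 12 under Table 3 |
|---|---|---|---|
| 0 days | 21/21 | 21/21 | 21/21 |
| ±3 days | 147/147 | 138/147 (94%) | 141/147 (96%) |
| ±7 days | 315/315 | 266/315 (84%) | 287/315 (91%) |

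An EOT on Day 65 becomes the Week 12 value in the primary analysis, while one on Day 64 is not used.

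**2. How many children.** About 90 are to be randomised (Protocol synopsis, Sample Size) and at least 80 are to complete 12 weeks (Protocol 4.2.3), which leaves about 90 - 80 = 10 non-completers. If EOT days are spread evenly over 84 treatment days (assumption), the share on Day 44-64 is 21/84 = 25%, and 10 × 0.25 = 2.5, so 2-3 children across both arms.

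**3. Whether the dropout analyses would run.** The trigger of more than 3% missing for imputation is met at 3 missing (3/90 = 3.3%; 3/80 = 3.75%). The trigger of more than 5% for the tipping-point and rank analyses is met at 5 missing (5/90 = 5.6%; 5/80 = 6.25%). Ten non-completers would pass both if their Week 12 scores are missing. The tipping-point analysis also needs a significant imputation result.

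**4. Size on the mean scale.** Shift in an arm mean = slope × worsening × k/45, where k is the number of affected children in the arm. The Week 6 to Week 12 slope of 0.7 and a worsening of 1-2 points are assumptions.

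- k = 1, 1 point: 0.7 × 1 × 1/45 = 0.016
- k = 2, 2 points: 0.7 × 2 × 2/45 = 0.062
- Extreme, k = 5, 2 points: 0.7 × 2 × 5/45 = 0.156

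**5. Size in the rank analysis.** I take non-completers to be ranked below completers, as the stated penalty implies. An exit score can then only reorder children within that lower set. If one OV101 child falls from the top to the bottom of the set, the net loss to the OV101 rank sum is at most the number of placebo children in it. With 5 non-completers per arm that is 5 ranks per affected child. The standard deviation of the rank sum, ignoring ties, is √(45 × 45 × 91/12) = 123.9. One child therefore moves z by at most 5/123.9 = 0.04, two by 10/123.9 = 0.08, and all five by 25/123.9 = 0.20. Ties raise these slightly.

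Two illustrations with assumed scores and 40 completers per arm agree with this. Both place every OV101 non-completer in the affected window, so they are high cases.

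- 5 versus 5 non-completers, OV101 scores changing from 3, 3, 3, 3, 4 to 5, 5, 6, 6, 6: z goes from 1.85 to 1.66 and p from 0.064 to 0.097.
- 3 OV101 versus 2 placebo non-completers: z goes from 1.79 to 1.73 and p from 0.074 to 0.083.

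**The case against.** The strongest answer is that the SAP already tests this record-selection choice. In the example, Table 3 enters the 6 as the Week 12 score in a full MMRM, with a matching model for the key secondary endpoints. That is harsher than using the 6 as a predictor. The nominal-visit analysis may do the same. This stands: a reader might infer that the exit score is lost from the whole plan, and the documents do not support that. What remains is narrower. Both analyses treat the exit score as if it were a Week 12 observation, and SAP 3.8.6 specifies the imputation, tipping-point and rank procedures under neither mapping.

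The existing checks also carry a penalty. The tipping-point analysis adds whole points to the imputed OV101 Week 12 values and leaves placebo alone, so an omitted 0.7-1.4 points (0.7 × 1 to 0.7 × 2) for an affected child is about one step. The rank analysis penalises leaving whatever score is used. Both points stand, and they are why the effect is modest.

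The exit rating has weaknesses of its own. It may be taken up to 14 days after the last dose and later than Day 43. An imputation slope estimated from completers' Week 6 scores may not transfer to it. This also stands, and it argues against replacing the planned imputation.

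**Conclusion.** The point holds as a modest gap in SAP 3.8.6. For a child who attends Week 6 and has an EOT on Day 44-64, the exit CGI-I-AS is normally absent from the primary MMRM, imputation, tipping-point and rank analyses, and no planned analysis uses it to rank the child or to inform the missing Week 12 score. The two-visit premise in SAP 3.8.6 also conflicts with SAP 3.1.8 and 3.8.1. Children who missed Week 6, or who stop drug but attend Week 12, are not affected.

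The expected size is 2-3 children in total and 0.02-0.06 points on an arm mean. This rests on 10 losses spread evenly over time, 1-2 affected children in an arm, 1-2 points of worsening and a 0.7 slope.

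Three stronger conclusions are tempting but not supported:

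- A reader might infer that the dropout checks favour OV101. The same rule drops placebo exit scores, and the documents do not show which arm would have more exits for worsening, so the direction is unknown.
- A reader might take 0.16 points as the likely size. That needs 5 OV101 exits in this window, which is half of all planned losses in one arm and one quarter of the treatment period, each 2 points worse.
- A reader might infer that the primary analysis is wrong. Keeping the scheduled Week 6 rating for the Week 6 visit is defensible.

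**What to change.** In SAP 3.8.6, rank children without a Week 12 score on their latest CGI-I-AS before Day 65, including an early EOT rating, instead of the Week 6 score. In the same section, correct the statement that CGI-I-AS is assessed at only two visits so that it acknowledges early EOT and unscheduled ratings.

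Optionally, add one supplementary imputation and tipping-point run that uses the latest score before Day 65 as the prior-score predictor. Report it beside the planned run, not in place of it. Leave the primary MMRM and Table 2 unchanged.

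The cost is SAP wording and minor programming on ratings already due to be collected. The downside is the one noted above: the exit rating may be off drug and later than Day 43, so the supplementary imputation needs that caveat.

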3.8.3 Other Secondary Efficacy Endpoint Analyses

For each subject, the average of daily values for each [REDACTED] will be calculated for the following visit windows:

Table 4: Analysis Visit Windows for [REDACTED]

Assessment	Analysis Visit Window (Interval in Study Days)
Baseline	< Day 1
Week 6	≥ (Week 6 Visit date – 14 days) to ≤ (Week 6 Visit Date + 7 days); or ≥ Day 22 to ≤ (End of Treatment – 1 day), for subjects who early terminate before Week 6
Week 12	≥ (Week 12 Visit date – 14 days) to (Week 12 Visit Date - 1 day); or ≥ Day 65 to ≤ (End of Treatment – 1 day), for subjects who early terminate between Week 6 and Week 12

An average measure will be calculated using all available data in the above analysis windows as follows:

1. Calculate average of all observed weekday values (AVGWKD).
2. Calculate average of all observed weekend values (AVGWKE).
3. Within a visit, if both AVGWKD and AVDWKE are non-missing, then the final average for the visit is $AVGWKD * (5/7) + AVGWKE * (2/7)$.
4. Otherwise, the final average for the visit is set to the non-missing AVGWKD or AVGWKE.

An MMRM Analysis of Covariance (ANCOVA) model for the change from Baseline will be fitted for each [REDACTED] endpoint defined above with fixed effects for visit (Weeks 6 and 12), randomized treatment, the visit-by-treatment interaction, age group (randomization stratification variable: age 4 to 8 years versus age 9 to 12 years), region (randomization stratification variable: US versus outside US), and the corresponding Baseline as a covariate. An unstructured within-subject covariance structure will be specified as the first choice. If the model converges, the Kenward-

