As described in Section 3.8.3, MMRM Analysis of Covariance (ANCOVA) models for the change from Baseline will be fitted for each [REDACTED] endpoint with fixed effects for visit (Weeks 6 and 12), randomized treatment, the visit-by-treatment interaction, age group, region, and the corresponding Baseline as a covariate. Missing data will not be imputed in the main analyses, but MMRM models implicitly adjust for missing data under a missing at random (MAR) assumption.

[REDACTED]

Based on visit average values, if more than 5% but not more than 20% of [REDACTED] data are missing at Week 12, as sensitivity analyses for each [REDACTED] secondary endpoint, missing data will be imputed using a multiple imputation procedure under a MAR assumption as follows:

1. Missing Week 6 [REDACTED] data points will be imputed under a MAR assumption using a linear regression model with randomized treatment, age group, region, and the corresponding baseline as independent variables.
2. Missing Week 12 [REDACTED] data points will be imputed under MAR assumption using a linear regression model with randomized treatment, age group, region, and the corresponding baseline and Week 6 [REDACTED] variable as independent variables.
3. Thirty complete imputed datasets will be generated by repeating the above steps 30 times.
4. The primary MMRM analysis of each [REDACTED] endpoint as described above will be performed for each of the 30 complete imputed data sets.
5. The estimated treatment effects will be combined across the 30 analyses using SAS PROC MIANALYZE.

If there is more than 20% of data missing for [REDACTED] endpoints, then baseline characteristics (including Baseline CGI-S-AS) will be compared for the subjects missing the specific [REDACTED] endpoint versus the subjects who are not missing the specific [REDACTED] endpoint, for both treatment groups combined. In this analysis, Baseline CGI-S-AS will be summarized as a continuous variable, with the focus on the mean if the normality assumptions are met for Baseline CGI-S-AS, and the focus on the median if Baseline CGI-S-AS is non-normal. Also, if the prevalence of missing is similar across treatment groups, CGI-I-AS at Week 12 will also be summarized by missing status and treatment group. These analyses will inform the interpretation of the descriptive analysis of the [REDACTED] endpoints.

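### For the redacted secondary endpoints analysed by MMRM ANCOVA, the one planned analysis that fills in missing visits repeats the MMRM's missing-at-random assumption, so it cannot show whether the result depends on that assumption

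*SAP*

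**What the plan says.** **Main analysis.** SAP 3.8.3 and 3.8.6 fit an MMRM ANCOVA to change from baseline. Its terms are visit, randomized treatment, "the visit-by-treatment interaction, age group, region, and the corresponding Baseline as a covariate". On the covariance, 3.8.3 says "An unstructured within-subject covariance structure will be specified as the first choice". On missing values, 3.8.6 says "MMRM models implicitly adjust for missing data under a missing at random (MAR) assumption".

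**Sensitivity analysis.** When more than 5% and not more than 20% of Week 12 visit averages are missing, 3.8.6 says "missing data will be imputed using a multiple imputation procedure under a MAR assumption as follows". Week 6 gaps are filled by a "linear regression model with randomized treatment, age group, region, and the corresponding baseline as independent variables". Week 12 gaps are filled by a "linear regression model with randomized treatment, age group, region, and the corresponding baseline and Week 6" value of the same endpoint. Then "Thirty complete imputed datasets will be generated by repeating the above steps 30 times", the same MMRM is fitted to each dataset, and the results are pooled.

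**Other provisions for these endpoints.** SAP 3.8.3 allows an optional analysis restricted to visit averages built on at least 3 days of data. Above 20% missing, 3.8.6 compares baseline characteristics of children with and without the endpoint. If missingness is similar across arms, it also summarises Week 12 CGI-I-AS by missing status and arm.

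**Contrast with the primary endpoint.** For CGI-I-AS, 3.8.6 accepts that Week 12 data missing after withdrawal may not be MAR. After the MAR imputation it says "additional sensitivity analyses using a tipping point approach will be performed under scenarios assuming missing not at random (MNAR"). It also adds a rank-based analysis that penalises discontinuation.

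**The concern.** A missing-data sensitivity analysis is useful if it changes the assumption about the unseen values and shows how far the answer moves. Here the assumption stays the same, no auxiliary variable is added, and the analysis model is the same. Two similar results in the study report could be read as evidence that missing data do not matter, although their agreement largely follows from the specification. If OV101 children with missing Week 12 values did worse than MAR predicts, both estimates would be too favourable by about the same amount, and nothing planned would reveal it.

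The stakes are limited. Under SAP 3.1.3 and protocol 7.12 these endpoints have no formal testing and their p-values are descriptive. The effect is on how the estimates and confidence intervals are read.

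**Working it through.** The documents give no numerical figure for this point, so there is none to reproduce. The check has two parts.

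**1. The two specifications side by side**

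| Element | Main MMRM | Planned imputation |
|---|---|---|
| Assumption | MAR | MAR |
| Treatment, age group, region, baseline | in the model | in both regressions |
| Week 6 information for Week 12 | through the within-subject covariance | as a predictor |
| Auxiliary variable | none | none |
| Final model | MMRM | same MMRM |

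The CGI-I-AS imputation does add one variable, the baseline CGI-S-AS overall score. The imputation for these endpoints does not.

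**2. Simulation**

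From the documents: 90 subjects, 45 per arm (SAP 2.2.1); the model terms and imputation steps above; 30 imputations; unstructured covariance. Assumed: residual SD 1, Week 6 to Week 12 correlation 0.6, true Week 12 effect 0.5 SD (coded so that larger is better), Week 12 missingness of about 6%, 10% and 20% weighted 2:1 towards OV101 and towards worse Week 6 values, and 2 intermittently missing Week 6 values. In the MNAR scenario the unseen Week 12 values of OV101 children are 1 SD worse than MAR predicts. There were 400 simulated trials per scenario.

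Mean Week 12 effect in the MNAR scenario:

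| Missing | MMRM | MAR imputation | Full data | Bias, MMRM / imputation | Imputation with 1 SD shift |
|---|---|---|---|---|---|
| 6% | 0.491 | 0.492 | 0.422 | 0.069 / 0.070 | 0.422 |
| 10% | 0.490 | 0.490 | 0.363 | 0.127 / 0.127 | 0.365 |
| 20% | 0.490 | 0.492 | 0.244 | 0.246 / 0.248 | 0.242 |

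Agreement between MMRM and MAR imputation at 6%, 10% and 20%:
- correlation across trials: 0.998, 0.997, 0.994;
- SD of the per-trial difference: 0.012, 0.016, 0.026, against a standard error of the effect of 0.217 to 0.230;
- same side of p = 0.05: 98.8%, 97.8%, 95.3% of trials.

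When MAR was true at 20% missing, the MMRM and imputation estimates were again 0.490 and 0.492, with a full-data value of 0.493. The observed data are the same in both scenarios; only the unseen values differ. Neither analysis can therefore tell the scenarios apart.

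**Arithmetic check.** Bias is approximately (share missing on OV101) × (departure in SD). With an exact 2:1 split:
- 6%: 5 missing, 5 × 2/3 = 3.3 on OV101, 3.3/45 = 0.07;
- 10%: 9 missing, 6 on OV101, 6/45 = 0.13;
- 20%: 18 missing, 12 on OV101, 12/45 = 0.27.

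These are close to the simulated 0.07, 0.13 and 0.25. The simulated values are slightly lower because missingness also leaned towards worse Week 6 values, which are less common on OV101. With missingness equal in both arms, the same product gives 0.05 to 0.20 SD per 1 SD departure over the 5% to 20% range.

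The last column recovers the full-data value because the shift equals the simulated departure. It shows only that a shift analysis responds to such a departure.

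**The case against.** **The endpoints are descriptive and no rule is broken.** This stands. Protocol 7.13 ties MNAR imputation and a tipping point to the primary endpoint. The SAP is graded: MNAR work for the primary, MAR imputation here, and no imputation for the remaining secondary endpoints (3.1.6.1). A reader might infer a departure from the protocol; the documents do not support that.

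**The two analyses are not identical.** This also stands. The MMRM holds age, region and baseline effects constant across visits, while the imputation regressions let them differ. The MMRM may fall back to a structured covariance, which the imputation does not impose. FAS membership depends on CGI-I-AS, so a child with no post-baseline value of the endpoint adds no outcome to the MMRM but can be imputed. It would therefore be too strong to say that the results must coincide. None of these differences relaxes MAR.

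**Other analyses exist.** They do, but the 3-day restriction addresses sparse data within a visit, and the comparison above 20% missing does not re-estimate the treatment effect.

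**Missing need not mean dropout.** Correct. The endpoints are averages of daily values, which may be absent for a child still in the study. Table 4 lets some early terminators contribute, and protocol 4.2 encourages continued visits after stopping drug. A reader might infer that OV101 dropouts will do worse and that the result will be biased; the documents give no evidence of that.

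**Redaction may hide an MNAR step.** This is unlikely. All five imputation steps are legible, and 3.1.6.1 mentions a tipping point for the primary endpoint but only multiple imputation for these.

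**Conclusion.** The point holds as a limited gap. Between more than 5% and 20% missing, the only planned analysis that re-estimates the effect with missing visits filled in keeps the MAR assumption of the main model. It will closely reproduce the main estimate and cannot test that assumption.

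The near-agreement follows from the matching specifications. The bias sizes do not: they rest on the assumed 1 SD departure, the 2:1 imbalance and the other simulation inputs, and they scale with the departure and the share missing on OV101. They show what could go unnoticed and do not predict this trial's result. The primary and key secondary conclusions are unaffected. The change is worth making because it is cheap and replaces an uninformative check with one that can respond to departures from MAR.

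**What to change.** In SAP 3.8.6, for these endpoints:

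1. Keep the 30 MAR-imputed datasets, but describe that step as a check on the MMRM fit.
2. Add a delta-adjusted analysis on the same datasets. Worsen the imputed Week 12 values of OV101 subjects over a prespecified grid (for example steps of 0.25 baseline SD, with the upper limit fixed before unblinding), leave placebo values unchanged, refit the MMRM, and report the estimate and 95% CI at every step.
3. State for each endpoint which direction is worse.
4. Do not carry over the start and stop rules of the CGI-I-AS tipping point. It begins only if the imputed result is significant and ends when p reaches 0.05, which has no role for endpoints that are not formally tested.
5. In the same edit, align the upper trigger. SAP 3.1.6.1 says below 20%, while 3.8.3 and 3.8.6 include exactly 20%, a value that can occur (18 of 90).

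Cost: SAP wording, some programming that can reuse the shift logic planned for CGI-I-AS, and one more table per endpoint. No new data are needed.
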